An important clinical question with respect to glucocorticoid use is that of the minimum dose that can effectively suppress the immune system. The dosing regimens for glucocorticoids that are commonly used in clinical medicine are mostly arbitrary and based on historical precedent rather than on an objective assessment of their effects on the immune system.^{3,13} While the glucocorticoid receptor is nearly saturated at prednisone-equivalent doses in the high-dose range (30-100 mg/day),³ much higher doses are often used in the clinic, despite limited objective evidence that they are clinically better than a lower dose. To determine the extent to which the transcriptional response to a single dose of glucocorticoid varies by dose, we will randomize study participants into 1 of 2 dose groups: 1 mg/kg or 250 mg.³ The 1-mg/kg dose was selected because it is commonly used as a starting dose in multiple clinical settings, including in patients with moderate SLE disease activity. The 250-mg dose was selected because that was the dose used in our clinical study of healthy volunteers; administering the same dose to patients with

SLE will facilitate the use of data from the healthy volunteer study in the planned comparison of the genomic response to glucocorticoids between patients with SLE and unaffected controls.

2 Study Objectives

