2.1 Primary Objective

To understand the cellular and molecular response to glucocorticoids in individuals with SLE.

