15.1 Definition of the Study Endpoints

The primary endpoint of this study is a list of human protein-coding genes and non-coding RNAs (small RNAs and long non-coding RNAs) that are differentially expressed in response to glucocorticoids in patients with SLE, for each of the studied cell types and doses.

The secondary endpoints of this study are:

1. A comparison of the transcriptional response to glucocorticoids between the 2 dose groups.
2. A list of protein-coding and non-coding transcripts, their corresponding proteins, and molecular pathways representing the best candidates for targeted therapeutic alternatives to glucocorticoids.
3. Validation of the targets identified by functional studies.
4. For each cell type, a list of protein-coding or non-coding transcripts that are shared and a list of transcripts that are different, between patients with SLE and the previously studied healthy controls, at baseline or in response to glucocorticoids.

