15.3 Identification of Glucocorticoid-responsive Genes

To identify glucocorticoid-responsive genes, differential expression analysis for the RNA-seq and small-RNA-seq data will be performed in R, with the package DESeq2.⁴⁶

For each cell type, we will assess the level of variation in the baseline measurements by comparing the expression values on the day of the screening visit to the 0-hour (pre-infusion) values on the day of the glucocorticoid infusion. For participants who undergo a glucocorticoid taper, this analysis will contrast the pre- and post-taper patterns of gene expression. We will then perform differential analysis comparing each of the two post-infusion time points (2 hours and 4 hours) independently against the baseline. DESeq2 (section 15.6) adopts the method of Benjamini-Hochberg to adjust for multiplicity. We will draw conclusions based on the Benjamini-Hochberg adjusted p values, which control for the family-wise false discovery rate (FDR) in the presence of multiple comparisons. We will employ a cutoff FDR⁴⁷ value of < 5% to

select the transcripts that will be considered differentially expressed in each cell type at each time point. The resulting gene lists will be contrasted to determine, for example, which genes are uniquely differentially expressed in a specific cell type, or common to a specific hematopoietic lineage. They will also be used for pathway enrichment analysis, to determine the molecular pathways and biological functions that are most responsive to the glucocorticoid stimulus in each cell type.

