15.6 Adaptive Sample Size Determination

Given the high-throughput data generation strategy of next-generation sequencing, the use of different starting materials for sequencing (mRNA, small RNA, DNA), and the use of serial sampling, standard sample size calculation methods are not appropriate in this case and an adaptive study design is a more realistic approach. Sample size consideration will be based primarily on the power to identify differentially expressed genes. The primary endpoint of the study is a list of human protein-coding genes and non-coding RNAs that are differentially expressed in response to glucocorticoids in patients with SLE, for each of the studied cell types and doses. With a sample size of 20 in each dose group, there would be 90% power to detect a change of effect size 0.72 before and after glucocorticoid by the standard paired t-test. That means, within each dose arm and for each cell type, we could detect a differentially expressed gene with 90% power if the gene expression difference before and after glucocorticoid was no less than 0.72 SD.

Due to the specific properties of RNA-seq data, an advanced mixed-effects negative binomial modeling approach will be adopted for evaluating gene expression change and the significance of the change. This will be achieved with the R package DESeq2, a widely adopted tool for differential expression analysis on sequencing data, which targets the issue of large number of genes and small number of samples. In DESeq2, data from all genes are shared and utilized in assessing the differential expression of each gene. This leads to more stable estimation of differential expression and its variability, and consequently to better power for detecting differentially expressed genes.

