Based on the data from our previous study of healthy volunteers (protocol 16-I-0126) and a bootstrap procedure, with a sample size of 20 we can detect differentially expressed genes from 0 to 2 hours after glucocorticoid infusion with a median of 0.45 log₂ fold change at a significance level of 0.05 after adjusting for multiplicity, and 0.62 log₂ fold change from 0 to 4 hours. In SLE patients, there may be higher variability in the data than what we observed in healthy volunteers. Meanwhile, the magnitude of gene expression changes is also expected to be higher, given the state of activation of many immune cells in SLE compared to healthy controls. Therefore, we estimate that the proposed initial sample size in this study will be sufficient to detect the genes associated with the effect of glucocorticoids in SLE patients.

To empirically evaluate whether this estimate is correct, we propose an adaptive study design similar to the one we performed on the study with healthy volunteers. Specifically, we will

recruit an initial cohort of 20 participants in each dose group. Based on the observed data from 20 participants, we will then assess the gain in discovery with up to 30 additional participants per group. We will perform a bootstrap procedure, sampling with replacement up to 50 units from the 20 observed participants in each group to evaluate the improvement in gene detection. For example, if the subset of genes that can be detected as differentially expressed over time and the subset of genes that can be detected as differentially expressed over the 2 doses do not change significantly above a number, then we will stop at that number. If there is change in the gene subsets, but the pathways and the biological interpretation of the data remain unchanged, then additional participants will be unlikely to change the outcome of the study and no further recruitment will be pursued. Due to the adaptive sample size determination, we will again use a nominal significance level $\alpha < 0.05$.

16 Ethics/Protection of Human Subjects

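### No specified contrast estimates the glucocorticoid response from all 40 participants; if the two doses act alike, a supportive dose-averaged contrast would cut the detectable effect by about 30%

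*Combined protocol and SAP*

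**What the plan says.** The primary objective (section 2.1) reads "To understand the cellular and molecular response to glucocorticoids in individuals with SLE". Whether the response differs by dose is a separate, secondary objective (section 2.2).

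The primary endpoint (sections 3.2.1 and 15.1) is a list of differentially expressed transcripts "for each of the studied cell types and doses". The power statement in section 15.6 follows the endpoint: "With a sample size of 20 in each dose group, there would be 90% power to detect a change of effect size 0.72" SD "before and after glucocorticoid by the standard paired t-test", and it adds that "within each dose arm and for each cell type, we could detect a differentially expressed gene with 90% power".

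Section 15.3 compares 2 h and 4 h with baseline in each cell type and selects transcripts at FDR < 5% by cell type and time point: "We will draw conclusions based on the Benjamini-Hochberg adjusted p values". It does not say whether the arms are fitted separately, jointly or pooled. It then describes a separate comparison of the high-dose and low-dose groups at the same time point.

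The interim bootstrap in section 15.6 resamples up to 50 units from the 20 participants in each group. It tracks both the genes changing over time and the genes differing between doses.

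**The concern.** Each participant supplies a pre-infusion control, so both arms carry information on the before/after change. Section 1.3 describes the receptor as close to saturation at prednisone-equivalent doses of 30-100 mg/day, so many genes may respond similarly in both arms. For those genes, a list built from 20 people uses half of the available information on the dose-free question.

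Two things are at stake. The first is sensitivity: at the strictness that FDR control implies, an arm of 20 may miss many genes that change by 0.72 SD. The second is readability: two low-powered lists disagree by chance, and a reader who sets them side by side may take the disagreement for dose-specific biology. Section 15.3 also leaves open which fit produces which list.

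**Working it through.** **Inputs.** From section 15.6: n = 20 per arm, 40 in total, d = 0.72 SD of the paired change, power 90%. Alpha is not given beside that figure. Two-sided 0.05 is assumed, in line with the nominal level named at the end of the section. From section 15.3: selection at BH FDR < 5%. The number of transcripts tested is not given.

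**1. The plan's figure.** Normal approximation: power = Φ(d√n − 1.96) = Φ(0.72 × 4.472 − 1.96) = 0.896. This matches the stated 90%. The paired t-test that the plan names, computed with the noncentral t (19 df, noncentrality d√n), gives 0.863; 90% power then needs 0.764 SD.

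**2. Dose-averaged contrast on 40, equal effects and SD.** The average of the two arm means has variance σ²/40, so the noncentrality is d√40 on 38 df. At alpha 0.05 the power is 0.993. The effect detectable with 90% power falls from 0.764 to 0.526 SD, or 31%. The normal approximation gives 0.725 to 0.513, or 29% (the factor 1/√2).

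**3. At FDR-type thresholds.** If a share π of genes responds and average power is 0.8, BH at 5% acts like a per-gene alpha of 0.05 × π × 0.8 / ((1 − π) × 0.95). That is 0.0004 at π = 1% and 0.0047 at π = 10%. Both shares are assumptions. Power at 0.72 SD, and the effect detectable with 80% power:

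| Per-gene alpha | Power, n = 20 | Power, 40 averaged | 80% detectable, n = 20 | 80% detectable, 40 |
|---|---|---|---|---|
| 0.005 | 53% | 93% | 0.91 SD | 0.61 SD |
| 0.001 | 30% | 83% | 1.08 SD | 0.70 SD |
| 0.0005 | 23% | 76% | 1.15 SD | 0.74 SD |

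**4. Reading the two per-dose lists together.** Take a gene with the same 0.72 SD response in both arms and per-arm power p. The chance of being on at least one list is 1 − (1 − p)². This gives 78%, 51% and 40% at the three thresholds, below the averaged contrast each time. Among such genes that are listed at all, the share on one list only is 2p(1 − p) / (1 − (1 − p)²), or 64%, 82% and 87%.

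**5. Unequal effects.** Let one arm have 0.72 SD and the other r times that. The average is then 0.72(1 + r)/2. At alpha 0.05, against 0.863 for the stronger arm alone:

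| r | 1 | 0.5 | 0.25 | 0 | −1 |
|---|---|---|---|---|---|
| Power, averaged | 0.993 | 0.914 | 0.792 | 0.602 | 0.050 |

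The averaged contrast equals the stronger arm's own test at r = 0.38 for alpha 0.05 (0.41 by the normal approximation), and at r = 0.34, 0.31 and 0.30 for alphas 0.005, 0.001 and 0.0005.

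**The case against.** A reader might infer that half the sample goes unused, or that no contrast uses all participants. The documents do not support either. Each arm's 20 feed that arm's list, the two sets of lists together are the stated primary endpoint, and the between-dose comparison uses both arms. What is missing is narrower: an estimate of the common response.

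A reader might also infer that averaging is free and should become the main result. It is not free, as step 5 shows. Sections 1.1 and 1.3 present similarity of the doses as an open question that the study is meant to examine, so a main list resting on that similarity would assume the answer. It would also displace the declared primary endpoint. And 250 mg was chosen to match the healthy-volunteer study, so that descriptive comparison needs the list for that dose.

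Nor do the documents show that dose-specific genes will be read from list overlap: section 15.3 contrasts lists by cell type and lineage and tests dose directly. Step 4 is a risk for readers of the lists, not a planned inference. The same holds for excess recruitment. The interim rule also considers between-dose genes and stops if pathways and interpretation are unchanged, so a stable averaged list would not by itself show that 40 people suffice.

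Finally, the lower end of the power range is pessimistic. Section 1.1 reports 10,665 responsive transcripts in vitro, 5,184 in one cell type only and 23 in all nine; the other 5,458 respond in at least two. That is at least (5,184 + 2 × 5,458 + 9 × 23)/9, or about 1,800 per cell type, and 1% responding would then mean over 180,000 transcripts tested. A paired t-test also ignores the sharing of information across genes in DESeq2, and section 15.6 separately cites a multiplicity-adjusted bootstrap from the healthy-volunteer study. These points stand. They temper the size of the gain, not its direction when the doses act alike.

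**Conclusion.** The point holds as a gap in specification. The objective names no dose, the endpoint and power are per arm of 20, section 15.3 does not say how the arms are modelled, and no specified contrast estimates the response from all 40.

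If the two doses have similar effects and SDs, averaging cuts the detectable effect by about 30% and raises power at 0.72 SD from 86% to 99% at alpha 0.05. The FDR-type figures are illustrative because the transcript count is not given and the model is a paired t-test, not DESeq2. All figures are for the initial 20 per group. The gain supports adding an averaged contrast beside the per-dose lists. It does not support replacing them.

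**What to change.** In section 15.3:

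- Fit one model per cell type with participant as a blocking term, time, and time-by-dose, using both arms.
- Keep the per-dose 0-2 h and 0-4 h lists as the primary endpoint and take them from this fit.
- Take the dose comparison from the time-by-dose interaction, so that it compares changes from each participant's own baseline and not levels at one time point.
- Add the dose-averaged 0-2 h and 0-4 h contrasts as a prespecified supportive list with its own FDR statement.
- State which contrast yields which list, and that presence on only one per-dose list is not evidence of a dose difference.

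In section 15.6, report the averaged list alongside the others in the bootstrap projection.

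The cost is analysis wording and one more set of tests per cell type and time point; no new participants or samples are needed, and the primary endpoint is unchanged. The write-up should say that the averaged list describes neither dose alone, can include a gene that does not respond at one of the doses, cancels opposite effects, and is the weaker test when the smaller effect is below roughly 0.3 to 0.4 of the larger.

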A separate analysis will compare data obtained at the same time point (2 hours or 4 hours) between the high-dose and low-dose groups, to test whether there are significant differences in the transcriptional effect of glucocorticoids at the two doses. Finally, we will identify differences and similarities between the baseline transcriptome and the transcriptional response to glucocorticoids in patients with SLE recruited in this study and in healthy volunteers recruited in our previous study. Since the healthy and the SLE participants come from two different studies, they are not directly comparable in many aspects. Therefore, these results will be derived from the two studies separately and no formal comparison will be made across the two studies. We will present the baseline distribution of gene expression, the distribution of gene expression changes, and the subset of differentially expressed genes. For each cell type, we will generate a list of protein-coding or non-coding transcripts that are shared and a list of transcripts that are different between SLE patients and healthy controls.

Sequencing library preparation and sequencing batches will be carefully designed such that samples from the same participant and cell type are run in the same batch and samples from different participants are evenly distributed across batches. This will keep batch effects to a minimum in the identification of differentially expressed genes. For analyses across different participants, such as comparisons among different cell types, linear regression will be adopted with batch as a regression variable to adjust for batch difference. While prior experience suggests that library preparation is the greatest source of batch-to-batch variation in RNA-seq experiments, if the source of batch effects is unclear or cannot be adequately modeled, then the R package SVA will be used.

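### The primary model is described as mixed-effects but assigned to DESeq2, which fits fixed effects only, and no participant term is stated; the dose comparison also leaves the pre-infusion sample unused

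*Combined protocol and SAP*

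**What the plan says.** Section 15.6 gives the sample-size argument on a within-person basis. For 20 participants per arm it claims "90% power to detect a change of effect size 0.72 before and after glucocorticoid by the standard paired t-test". It then restates the detection threshold for a single gene: "if the gene expression difference before and after glucocorticoid was no less than 0.72 SD". The next paragraph changes the method: because of the properties of RNA-seq data, "an advanced mixed-effects negative binomial modeling approach will be adopted". On implementation it says: "This will be achieved with the R package DESeq2".

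Section 15.3, which describes the analysis itself, says that DESeq2 will be used and that the contrasts are made by "comparing each of the two post-infusion time points (2 hours and 4 hours) independently against the baseline". It gives no design formula, participant factor or random effect. It does place one participant's samples of a given cell type in the same sequencing batch. Batch is the only regression variable it names, and only for analyses across participants.

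For the dose question, 15.3 says: "A separate analysis will compare data obtained at the same time point (2 hours or 4 hours) between the high-dose and low-dose groups". Secondary objective 2 and the first secondary endpoint (2.2, 3.2.2, 15.1) concern the transcriptional response to glucocorticoid, not the post-infusion level.

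**The concern.** A mixed-effects model carries the pairing through a random participant effect. The named tool has no random effects, so the sentence in 15.6 cannot be carried out as written. An analyst must either replace the random effect by a fixed participant block, drop it, or change software, and the plan does not say which. The first choice keeps the pairing. The second treats one person's samples before and after infusion as if they came from different people.

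The primary endpoint is the gene list itself, so list membership depends on this choice. The adaptive step in 15.6 also uses the detected gene subsets to decide whether to recruit beyond 20 per group, so the same unstated model feeds that decision.

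The dose comparison has a related but milder weakness. Each participant's 0-hour sample is available and the question is about response, yet the stated contrast uses post-infusion values alone.

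**Working it through.** **Inputs.** From 15.6: n = 20 per dose group, effect 0.72 SD, paired t-test, 90% power. The SD is taken as that of within-person differences, as a paired t-test implies. The significance level is not given beside the power figure, so two-sided 0.05 per gene, unadjusted, is assumed. The within-person correlation (rho) is not in the documents; 0.3 to 0.8 is assumed.

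**1. The plan's figure.** The noncentrality is 0.72 × √20 = 3.22. The normal approximation gives Φ(3.22 − 1.96) = 0.896, which reproduces the stated 90%. The exact noncentral t with 19 degrees of freedom gives 0.863. The 90% is therefore a paired figure.

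**2. Participant term left out.** Scale the SD of differences to 1. The per-sample variance is then 1/[2(1 − rho)]. An unpaired test takes the variance of the mean difference as (2/20) × 1/[2(1 − rho)] = 1/[20(1 − rho)], whereas the true variance is 1/20. Its standard error is too large by the factor 1/√(1 − rho). Approximately:

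- power = Φ(3.22 − 1.96/√(1 − rho))
- type I error = 2 × [1 − Φ(1.96/√(1 − rho))]

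The data are still correlated pairs, so a power formula for two independent groups does not apply. Simulating an unpaired t-test on 1,000,000 sets of 20 normal pairs at each correlation gives:

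| Assumed rho | Power, approximation | Power, simulated | Type I error, simulated |
|---|---|---|---|
| 0.3 | 0.81 | 0.78 | 0.02 |
| 0.5 | 0.67 | 0.64 | 0.007 |
| 0.7 | 0.36 | 0.35 | 0.001 |
| 0.8 | 0.12 | 0.15 | < 0.001 |

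The paired t-test on the same data has power 0.86 throughout.

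**3. Participant as a fixed block.** Negative binomial regressions were simulated (mean count 200, dispersion 0.08, 400 runs per setting, dispersion treated as known; a stand-in for DESeq2, not DESeq2 itself). With participant + time, power was 0.88 to 0.91 for rho from 0 to 0.7, and type I error 0.045 to 0.068. With time alone, power was 0.90, 0.82, 0.67 and 0.29 at rho 0, 0.3, 0.5 and 0.7. The block costs nothing relative to the plan's own calculation: 40 samples less 20 participant coefficients and 1 time coefficient leave 19 residual degrees of freedom, as in the paired t-test.

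**4. Dose contrast.** Each participant receives one dose, so fixed participant effects absorb the dose main effect. Within a participant-blocked model the dose question has to be the dose-by-time interaction. With equal variance σ² before and after infusion, the per-person variance that enters the dose comparison is:

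| Assumed rho | Post-infusion level, σ² | Change, 2σ²(1 − rho) | Baseline-adjusted, σ²(1 − rho²) |
|---|---|---|---|
| 0.3 | 1.00 | 1.40 | 0.91 |
| 0.5 | 1.00 | 1.00 | 0.75 |
| 0.7 | 1.00 | 0.60 | 0.51 |
| 0.8 | 1.00 | 0.40 | 0.36 |

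(Entries are multiples of σ².) The change contrast is less precise than the level contrast below rho = 0.5 and more precise above it. Baseline adjustment is better than both at every correlation shown.

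**The case against.** The best defence is that the intent is plain. Section 15.6 sizes the study on a paired test and calls the model mixed-effects. Section 15.3 keeps a participant's samples in one batch and brings in batch as a regressor only for comparisons across participants. A competent analyst would add participant as a block, and the plan nowhere proposes a fit of time alone. The limit on DESeq2 is also a fact about software that the documents do not state.

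Most of this stands. It rules out several stronger readings that a reader might infer:

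- *DESeq2 cannot do a paired analysis.* It can, with participant as a fixed block.
- *The gene list would fill with false positives.* With positive correlation the unpaired test is conservative (step 2), so the risk is missed genes.
- *Most of the power would be lost.* That depends on the correlation. Against 0.863, the share kept is 0.78/0.863 = 90% at rho 0.3 and 0.64/0.863 = 74% at 0.5. More than half is lost only at about 0.7 and above.
- *The dose comparison is invalid.* A same-time-point contrast between randomised groups is valid, and the stated power does not depend on it.

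The defence does not remove the mismatch itself. The blocked fit is a different model from the one written. Even setting the software fact aside, a paired power claim sits beside an analysis section in which no term carries the pairing.

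**Conclusion.** For the primary model, the plan is wrong as written: it names a model that its tool cannot fit and does not state the one that can. This is a defect of specification, not of design or data. With a participant block, the power stays near the plan's figure (0.86 by exact paired t; 0.88 to 0.91 in the negative binomial simulation). Without it, power for the same change would be about 0.78 to 0.15 as the correlation goes from 0.3 to 0.8, with type I error at or below about 0.02. These sizes rest on an assumed correlation, a per-gene unadjusted two-sided 0.05, and 0.72 read as SDs of the differences.

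For the dose comparison, the point is a cheap improvement. The stated contrast is sound but leaves each person's pre-infusion sample unused when the endpoint is a response.

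**What to change.** In 15.6, replace the mixed-effects wording by a DESeq2 negative binomial regression with design participant + time, fitted for each cell type and dose arm. If random participant effects are preferred, name a tool that fits them. Repeat the design in 15.3, and state that the bootstrap for the adaptive step uses the same model.

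In 15.3, test the dose question by the dose-by-time interaction with participant nested in dose, or by a comparison at each time point adjusted for the gene's own pre-infusion expression. The interaction has a downside: it is less precise than the present contrast if the correlation is below 0.5. Baseline adjustment avoids that, but it needs a covariate that differs by gene, so the tool for it should be named too.

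The cost is a few sentences in two sections. No new samples, visits or participants are needed. The healthy-volunteer data already used for planning (protocol 16-I-0126) include samples before and after infusion, so they could supply the within-person correlation and guide the choice for the dose contrast.
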